The warm-up included 13 exercises, performed in an average time of 8 to 10 minutes and in the same way during the eight weeks of intervention, while, in the fourth part of the session, final stretching or return to calm, the participants performed 8 exercises during the first 6 weeks of intervention and 10 exercises in the last two weeks. Each exercise was performed for 30 seconds, which took approximately 8 to 10 minutes to complete them. Finally, the neuromuscular component (static balance training with one-foot balance exercises) was performed after muscle strengthening exercises. It was based on 8 exercises, which changed every two weeks with a duration between 30 to 45 seconds each, and between one to two repetitions per exercise depending on the week of intervention. The three phases mentioned above were exactly the same for both treatment groups.

All participants participated in groups of four people per session, three exercise sessions per week for eight weeks in total, at the IPS-CAFAM (Institución Prestadora de Salud de la Caja de Compensación Familiar) Rehabilitation Center, for a total of twenty-four sessions, which were supervised by a Physiotherapist, who was responsible not only to verify the quality in the performance of each of the exercises, but to teach during the first two weeks of intervention (anatomical conditioning phase) the fundamental bases of adequate breathing and feed them back during all the intervention protocol, as well as guaranteeing a correct posture in performing the training and thus avoiding the appearance of low back pain as a result of a poor training technique, as well as the increase in intra-abdominal pressure generated by the “pushing” when it is not known to breathe properly during strength training.

The hydration of each participant was also crucial during each training session. Similarly and prior to the start of the protocol, all patients were instructed and suggested the importance of wearing appropriate footwear for training (sports sneakers, sportswear - during the first two weeks they were suggested to wear shorts to observe the position of the knees during the exercises and later the use of liquefied pants up to the ankle to avoid rubbing the elastic bands with the skin-; likewise, they were instructed to bring water bottle, towel to dry the sweat and not to use elements that could injure them during the exercise, such as bracelets or necklaces.

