To evaluate the effect of muscle strength on the alignment of the knees and analyze the effect of muscle strength on the unipodal balance, **Table 8** shows the deltas of the medians (changes or differences observed after the intervention) for each of the treatment groups and for each of the variables measured at the beginning and end of the intervention.

In this way, when they include or add exercises for the strengthening of the core, to the traditional treatment of SPF or anterior knee pain, the quality of life measured with the Kujala test in these patients increases, especially by the significant reduction of pain, highlighting for example, that for the total score of the Kujala test, there was a statistically significant difference ($p = 0.025$), with an increase of 5 points for group A (group A = 23.0, group B = 17.0), which indicates that the population of the study group improved their quality of life more after the intervention compared with the people of group B. A similar effect is observed in the increase of the strength of the core musculature for group A, especially in the oblique force evaluated with the side plate, with a difference of 30 seconds for group A, and only five seconds for group B on the left lateral plate, with a statistically significant p value (<0.001).

Therapeutic Effect of Two Muscle Strengthening Programs in Patients with Patellofemoral Pain Syndrome
On the other hand, the differences for the total pain evaluated with EVA were -6 and -4 for group B, with an interquartile range (-10; -4) and (-7; -3) respectively. Although p was not statistically significant, these differences were clinically relevant. For the hip and knee muscle strength, measured with the squat test, there was no statistically significant difference in the median of the deltas between the treatment groups, but there was one in each group, which means that all of them increased strength muscle in hips and knees, as a result of strengthening for these muscle groups.

Table 8: Effect of muscle strengthening on pain, knee alignment, core, hip and knee strength and balance by treatment groups.

Variable	Treatment A			Treatment B			Value p *
	Initial Medium (RI)	Final Medium (RI)	Delta Medium (RI)	Initial Medium (RI)	Final Medium (RI)	Delta Medium (RI)	
Pain (EVA)	7.5 (5.5-9.0)	2 (0-2)	-6 (-10; -4)	7.0 (5.5-8.5)	2.0 (0-4)	-4 (-7; -3)	0.058

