In **Table 9**, differences in medians and interquartile ranges their entire study population at the beginning and end of treatment for muscle strength, pain and level of physical activity is. It can be seen that the gluteal and quadriceps muscle strength measured with the squat test at the end of the treatment was the same in both groups, with a statistically significant p value (<0.001), which means that the whole population increased strength in a significant way.

In the same way, a similar effect was observed in the median pain measured with the VAS at the end of the treatment, because they all reported a decrease in pain, this difference being statistically significant, with a p-value less than 0.001. However, in the measurement of physical activity level with the long IPAQ at the end of the treatment, it was observed that the study population in group B spent less time practicing physical activity at the beginning of treatment, but both groups increased in time similar this practice at the end of the treatment; however, this difference was not statistically significant.

Table 9: Difference of intragroup medians for muscle strength, pain and physical activity level.

Variable	Treatment A			Treatment B		
	Initial Medium (RI)	Final Medium (RI)	Value p *	Initial Medium (RI)	Final Medium (RI)	Value p *
Squats	10.0 (8.0-18.5)	35.0 (30.0-38.0)	<0.001	12.5 (8.5-20.0)	35.0 (29.0-38.0)	<0.001
IPAQ (minutes)	3003 (1116-4638)	4275 (2587-6522)	0.029	1617 (944-6138)	4598 (2888-7344)	0.012
Pain (EVA)	7.5 (5.5-9.0)	2.0 (0.0-2.0)	<0.001	7.0 (5.5-8.5)	2.0 (0-4)	<0.001

* Wilcoxon nonparametric test

Muscular Strength and Static Balance

In **Table 10**, the correlation between the muscle and gluteus muscle strength differences measured with the squat and unipodal balance test evaluated with the One Leg Stance test with open and closed eyes by treatment groups is shown, with which it is emphasized that, for both treatment groups, the unipodal balance improved clinically significant. However, for the study group (A), this correlation was greater (strong), especially in the variable with open eyes for both lower limbs, indicating that by increasing muscle strength (glutes and quadriceps in this case) it is improved the unipodal balance. Although there is an increase in the balance for both treatment groups, there is a stronger correlation when core exercises are included, which is what happens in group A.

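### The effect of hip and knee strength on one-leg balance cannot be separated from the balance training that both arms received; the only randomised balance contrast is the addition of core exercises.

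*SAP*

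**What the plan says.** The SAP, under Post-Intervention Results, gives one purpose of Table 8 as to "analyze the effect of muscle strength on the unipodal balance". The table is titled "Effect of muscle strengthening on pain, knee alignment, core, hip and knee strength and balance by treatment groups". Its only p-values are Mann-Whitney comparisons of the changes between arms.

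Under Muscular Strength and Static Balance, Table 10 correlates squat gain with gain on the "unipodal balance test evaluated with the One Leg Stance test with open and closed eyes by treatment groups". The text reads the group A coefficients as showing that more gluteal and quadriceps strength improves one-leg balance, and says the correlation is stronger when core exercises are included.

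The Protocol (Intervention Protocol) describes a separate part of each session: "the neuromuscular component (static balance training with one-foot balance exercises) was performed after muscle strengthening exercises". On its content: "It was based on 8 exercises, which changed every two weeks with a duration between 30 to 45 seconds each", with one or two repetitions depending on the week. Of warm-up, stretching and this balance component it says: "The three phases mentioned above were exactly the same for both treatment groups". The SAP text after Table 8 adds that hip and knee strengthening was done identically in both arms.

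**The concern.** The outcome is time standing on one leg, and both arms trained one-foot balance for the whole program alongside the strengthening that is credited with the gain. To credit the strengthening, the trial would need patients who strengthened without balance practice, or arms that differed in hip and knee strengthening. It has neither.

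At stake is what a reader takes away. Balance rose a great deal in both arms, and the text offers hip and knee strength as the reason. The one balance question that randomisation does answer, whether adding core exercises changes one-leg balance, has its p-values in Table 8, but the text never states the answer.

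**Working it through.** The documents give no figure for this claim to reproduce. The check compares what each arm received, then asks what each analysis can show.

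**1. Components by arm**

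| Component | A | B | Source |
|---|---|---|---|
| Hip and knee strengthening | yes | yes, same | SAP, text after Table 8 |
| One-foot balance training | yes | yes, same | Protocol |
| Warm-up, stretching | yes | yes, same | Protocol |
| Core exercises | yes | no | SAP, text on Table 10 |

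Only the last row differs.

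**2. Amount of balance practice** (24 sessions: "three exercise sessions per week for eight weeks in total")

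- If all 8 exercises were done each session: 8 × 30–45 s × 1–2 repetitions = 240–720 s, or 4–12 min; × 24 = 96–288 min.
- If the 8 were spread over four two-week blocks, 2 per block: 2 × 30–45 s × 1–2 = 60–180 s, or 1–3 min; × 24 = 24–72 min.

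The Protocol sentence allows either reading. The figures show that practice was regular; they do not show how much of the gain it caused.

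**3. Within-arm change.** Right eyes closed, the median went from 4.5 to 28.5 s in A and from 5.25 to 23.5 s in B. Strengthening and balance practice were given together to everyone, so this rise cannot be divided between them.

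**4. Between-arm contrast in strength.** Median squat gain was 20.0 in A and 20.0 in B (p = 0.670), so there is no contrast in hip and knee strength to exploit. Core strength does differ: left side plank gain was 30.0 v 5.0 s (p < 0.001), with balance practice held equal.

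**5. Between-arm contrast in balance** (Table 8)

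SD per arm ≈ IQR width / 1.349, pooled as √((SD_A² + SD_B²)/2). The difference detectable with 80% power at two-sided 0.05 and 20 per arm is (1.960 + 0.842) × SD × √(2/20) = 0.886 × SD.

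| Measure | Median gain A, B (s) | A − B | p | SD (approx.) | Detectable (s) |
|---|---|---|---|---|---|
| Open, right | 11.5, 7.5 | +4.0 | 0.916 | 20.6 | 18.3 |
| Open, left | 9.5, 20.0 | −10.5 | 0.282 | 19.3 | 17.1 |
| Closed, right | 20.0, 19.0 | +1.0 | 0.671 | 10.4 | 9.2 |
| Closed, left | 24.5, 20.0 | +4.5 | 0.349 | 13.9 | 12.3 |

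Example, closed right: 13.5/1.349 = 10.0 and 14.5/1.349 = 10.7; pooled 10.4; × 0.886 = 9.2 s.

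Final eyes-open values are 45.0 (45.0–45.0) on both legs in both arms. If 45 s is the maximum (none is stated), about three quarters or more of each arm finished at it. For those patients the change is simply 45 minus the starting value.

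**6. Table 10 correlations.** 95% CI = tanh(atanh r ± 1.96/√17). A v B: z = (atanh r_A − atanh r_B)/√(2/17).

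| Measure | A: r (95% CI) | B: r (95% CI) | p, A v B |
|---|---|---|---|
| Open, right | 0.558 (0.15 to 0.80) | 0.121 (−0.34 to 0.53) | 0.14 |
| Open, left | 0.554 (0.15 to 0.80) | 0.110 (−0.35 to 0.53) | 0.13 |
| Closed, right | 0.390 (−0.06 to 0.71) | 0.009 (−0.44 to 0.45) | 0.24 |
| Closed, left | 0.008 (−0.44 to 0.45) | −0.244 (−0.62 to 0.22) | 0.45 |

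With the Bonett-Wright variance, better suited to Spearman coefficients, the last column becomes 0.15, 0.15, 0.25 and 0.46. The data do not establish a stronger correlation in A.

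**The case against.** A reader might go further and infer that the balance question cannot be answered at all, or that the arm comparison is biased. The documents do not support that. Identical practice in both arms leaves A v B unbiased for the effect of adding core exercises, and core strength clearly separated the arms. The limit applies to hip and knee strength, which is the strength the SAP's conclusion names.

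A reader might also infer that Table 8 hides the balance result. It does not: all four between-arm p-values are printed, and no within-arm test of balance is reported. What is missing is a statement of the result in the text.

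Nor should shared practice be blamed for the Table 10 correlations. A dose common to all patients does not by itself produce a correlation within an arm. Their weakness is that they are not randomised, rest on about 20 patients per arm, carry no intervals, and could reflect attendance or effort. The Protocol notes that about 15% of patients agreed that one of three weekly sessions could be at home.

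Two defence points stand in part. The Protocol does not say whether any balance drill was done eyes closed or resembled a timed stance, so the match to the test is close for one-foot balance in general but undocumented for eyes closed. And the Table 8 title can be read as naming the whole program, since the Protocol sometimes uses strengthening program in that sense. Neither point rescues the sentence on gluteal and quadriceps strength, because no arm received strengthening without "static balance training with one-foot balance exercises".

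**Conclusion.** The point holds for hip and knee strength. Both arms received the same strengthening and the same balance training, squat gain was 20.0 in each, and so neither the pre-post gains nor the A v B comparison can show that this strength improves One Leg Stance time. The Table 10 correlations do not fill the gap.

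The randomised effect of adding core exercises can be estimated, but coarsely. The observed median differences (−10.5 to +4.5 s, mixed in sign) are all below the detectable differences of about 9 to 18 s. The right summary is that no difference was shown; absence of an effect was not shown either.

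Assumptions: 20 patients per arm contribute final measurements (20 is the Table 5 figure; Table 8 gives no numbers); SDs are taken from IQRs although the changes were reported as non-normal, so the detectable differences are rough; and the eyes-open ceiling is inferred. The core conclusion depends on none of these, because it follows from the components each arm received.

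**What to change.** 1. Restate the balance objective in the text introducing Table 8 as the effect of adding core exercises on one-leg balance when both arms also receive balance training.
2. State in the text the A v B difference in change for each of the four measures, with an estimate and 95% confidence interval (a Hodges-Lehmann shift would match the Mann-Whitney test). Say that none was significant (p = 0.916, 0.282, 0.671, 0.349) without claiming no effect. Note the apparent eyes-open ceiling, and give the test maximum if there was one.
3. Retitle Table 8 as the effect of the exercise programs, keeping the balance rows, and attribute pre-post balance gains to the whole program, balance drills included.
4. Withdraw the statement under Muscular Strength and Static Balance that gaining gluteal and quadriceps strength improves balance. Present Table 10 as exploratory and non-randomised, with the number of patients and confidence intervals, and drop the claim that core exercises made the correlation stronger.

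The cost is some rewording and a few intervals from data already held. The downside is giving up a favourable explanation of the balance gains.

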[name]

NCT04011436

Therapeutic Effect of Two Muscle Strengthening Programs in Patients with Patellofemoral Pain Syndrome

**Therapeutic Effect of Two Muscle Strengthening
Programs in Patients with Patellofemoral Pain
Syndrome from Bogota, Colombia.
Experimental Study, Clinical Controlled Trial.**

NCT: 04011436

Date of creation: July 1, 2018.

PROCESSING AND DATA ANALYSIS.

For the classification and verification of the information, the database was refined by recoding and labeling the variables necessary for the analysis, in addition, the variables that required it were converted to alphanumeric format and the review of extreme non-plausible data was performed. For the continuous variables in which two attempts were made as balance and plate a new variable was generated with the average of the measurements and in this way obtain the final result for the analyzes.

Univariate Analysis

The report of absolute and relative frequencies was made; the qualitative variables were presented in proportions and 95% confidence intervals. The normality of the continuous variables was evaluated by scatter plots (histograms, Kernel density and Q-Norm) and the numerical test of Shapiro-Wilk, and according to their distribution they were reported as means and standard deviations, when they had a distribution normal, or on the contrary, as medians and interquartile ranges.

Bivariate Analysis

In the bivariate analysis, a comparison of each of the Kujala test domains was initially performed to assess pain in the baseline, assessing the differences between the intervention groups using the chi-square or Fisher's exact tests. Additionally, the Spearman correlation coefficient was used to evaluate the relationship between two continuous variables, such as the Q angle and the anterior knee pain, evaluating the correlation in a marginal and conditioned way to each of the treatment groups.

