Later, to evaluate if there were differences between the groups of treatment after the intervention on the variables of interest, deltas were generated from the Kujala test, EVA, number of squats, Q angle, balance, physical activity and core strength. with iron and trunk extension, evaluating normality by means of graphic and numerical methods. For the analysis of the differences of medians between the groups, taking into account that the outcomes did not present a normal distribution, and assuming the assumption of independence of the variables, we proceeded to use the non-parametric Mann-Whitney U test. Finally, through the Wilcoxon test, intragroup differences were evaluated for strength, pain and physical activity components.

The hypothesis tests were presented in two tails with an alpha of 0.05 and all the analyzes were executed with the statistical program STATA version 14.0.

BASELINE:

Study population

Therapeutic Effect of Two Muscle Strengthening Programs in Patients with Patellofemoral Pain Syndrome

Table 5 describes the general characteristics of the study population at baseline. There were no significant differences between the two intervention groups (A and B), which means that the randomization was adequate; however, in the total score of the Kujala test there was a difference of 12.5 points between the groups, with a lower score for group B (53.0), which indicates better core strength for these patients. Finally, the sex variable was defined as categorical and the rest of the variables as continuous, for which the medians and their respective interquartile range (IR) are reported, taking into account that the variables did not have a normal distribution.

Table 5: Baseline variables of the study population

Variables	Treatment A (n 20) Medium (RI)	Treatment B (n 20) Medium (RI)	Value p ^a
Sex * (Male, Ref)			
Female	90 (65.7-97.6) *	90.0 (65.7-97.6) *	1,000 ^b
Age	32.5 (25.5-38.0)	29.0 (25.0-36.5)	0,569
Initial weight (Kg)	64.6 (55.3-72.4)	62.7 (52.9-68.5)	0.379
Size (cm)	160 (156.5-167.0)	159.5 (154.0-163.0)	0.423
IMC	25.4 (21.5-27.9)	23.8 (22.3-25.2)	0.456
% of fat	35.4 (28.9-40.4)	35.4 (24.5-38.7)	0,714
% muscle	26.9 (24.5-28.9)	26.2 (24.6-29.0)	0.849
Visceral fat	6 (3.5-7.09)	5 (4.0-6.0)	0.433
IPAQ (minutes)	3003 (1116-4638)	1617 (944-6138)	0,588
Pain	7.5 (5.5-9.0)	7.0 (5.5-8.5)	0.764
Kujala total score	65.5 (42.5-72.5)	53.0 (44.5-71.5)	0,892
Q angle			
Straight	19.0 (15.0-20.0)	18.0 (15.0-20.0)	0,557

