Kujala total test score	65.5 (42.5-72.5)	88.0 (81.0-95.0)	23.0 (16.0-37.0)	53.0 (44.5-71.5)	78.0 (64.0-88.0)	17.0 (8.0-24.0)	0.025
Squats	10.0 (8.0-18.5)	35.0 (30.0-38.0)	20.0 (18.0-25.0)	12.5 (8.5-20.0)	35.0 (29.0-38.0)	20.0 (15.0-24.0)	0.670
IPAQ (minutes)	3003 (1116-4638)	4275 (2587-6522)	1539 (807-2457)	1617 (944-6138)	4598 (2888-7344)	1977 (1191-2815)	0,492
Q angle							
Straight	19.0 (15.0-20.0)	18.0 (15.0-20.0)	0 (-2; 2)	18.0 (15.0-20.0)	18.0 (15.0-20.0)	0 (-2; 2)	0.819
Left	18.0 (15.0-20.0)	18.0 (16.0-20.0)	0 (-2; 2)	18.0 (15.0-20.0)	18.0 (15.0-20.0)	0 (-2; 2)	0.672

Balance with open eyes							
Straight	30.0 818.25- 45.0)	45.0 (45.0- 45.0)	11.5 (0- 25.5)	40.0 (18.25- 45.0)	45.0 (45.0- 45.0)	7.5 (0- 30.0)	0.916
Left	29.5 (15.75- 44.0)	45.0 (45.0- 45.0)	9.5 (0- 21.5)	25.75 (14.5- 45.0)	45.0 (45.0- 45.0)	20.0 (0- 30.0)	0.282
Balance with closed eyes							
Straight	4.5 (3.0- 9.259)	28.5 (21.0- 35.0)	20.0 (14.0- 27.5)	5.25 (3.0- 7.25)	23.5 (16.5- 31.5)	19.0 (9.5- 24.0)	0.671
Left	5.0 (3.0- 8.7)	30.0 (23.5- 38.0)	24.5 (13.0- 30.5)	4.25 (3.5- 7.259)	27.5 (14.0- 34.5)	20.0 (10.5- 30.5)	0.349
Griddle	20.5 (12.0- 32.0)	60.0 (45.0- 70.0)	37.0 (24.0- 48.0)	30.0 (13.5- 33.5)	35.0 (20.0- 60.0)	10.0 (2.0- 15.0)	<0.001
The t. Right	15.0 (10.0- 21.0)	45.0 (38.0- 51.0)	30.0 (19.0- 36.0)	15.0 (9.5- 20.0)	22.0 (16.0- 38.0)	6.0 (2.0- 12.0)	<0.001
The t. Left	12.5 (10.5- 19.0)	45.0 (36.0- 56.0)	30.0 (17.0- 40.0)	18.0 (11.0- 23.0)	21.0 (15.0- 34.0)	5.0 (-2 - 10.0)	<0.001
Trunk extension	13.5 (6.0- 26.5)	61.0 (50.0- 75.0)	49.0 (30.0- 55.0)	13.5 (2.5- 20.0)	30.0 (15.0- 60.0)	15.0 (7.0- 34.0)	0.001

* U of Mann-Whitney for the delta of the measurements between the groups.

He was also interested in this research, to observe the intra-group differences of including hip and knee muscle strengthening exercises (conventional physiotherapeutic treatment) performed in the same way for both intervention groups, as mentioned in the description of the strengthening protocol.

Intragroup differences

Therapeutic Effect of Two Muscle Strengthening Programs in Patients with Patellofemoral Pain Syndrome

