Table 10: Correlation between differences in muscle strength and balance by treatment groups

Therapeutic Effect of Two Muscle Strengthening Programs in Patients with Patellofemoral Pain Syndrome

Variable	Squats	
Balance	Treatment A *	Treatment B *
Right with open eyes	0,558	0.121
Left with open eyes	0,554	0.110
Right with closed eyes	0.390	0.009
Left with closed eyes	0.008	-0.244

* Spearman correlation coefficient.

With the previously stated results, the alternative hypothesis of this study is rejected, which means that adding core exercises to traditional hip and knee muscle strengthening for the treatment of anterior knee pain in patients diagnosed with SPF is more effective in reducing pain and improving the quality of life of these people, they do only hip and knee strengthening exercises.

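### Open-eyes balance appears to sit at a 45 s limit at the end of treatment, so the open-eyes correlations in Table 10 are weak ground for the strength-balance conclusion

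*SAP*

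**What the plan says.** The data-processing section of the SAP averages repeated attempts: "two attempts were made as balance and plate a new variable was generated with the average of the measurements". The available text gives no maximum time for the one-leg stance and no number of patients measured at the end. Table 5 gives baseline numbers only ("Treatment A (n 20", and 20 in B).

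Table 8 (Post-Intervention Results) reports final open-eyes balance as 45.0 (45.0-45.0) on both legs in both arms. In three of the four cells the baseline upper quartile is already 45.0, so the row runs "45.0) 45.0 (45.0"; in the fourth (A, left) it is 44.0. The between-arm test is described as "U of Mann-Whitney for the delta of the measurements between the groups", with p = 0.916 (right) and 0.282 (left). On significance the SAP says "The hypothesis tests were presented in two tails with an alpha of 0.05".

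The section on Muscular Strength and Static Balance then reads Table 10, whose first row is "Right with open eyes". It calls the correlation with squat gain strong in A, "especially in the variable with open eyes for both lower limbs". It infers that more strength brings better balance, and adds that "there is a stronger correlation when core exercises are included".

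**The concern.** A timed measure whose median and both quartiles are the same round number in four separate cells has almost certainly hit a stopping time. For a patient who finishes at that limit, the change score is fixed by where the patient started: delta = 45 minus baseline. A correlation between squat gain and that delta is then close to a correlation between squat gain and baseline balance deficit. The SAP reads it as evidence that strength gain drives balance gain.

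Two readings are at stake. The open-eyes p-values might be taken to show that the arms had the same balance outcome. The open-eyes coefficients in A are the emphasised support for a claim about mechanism and about the added value of core exercise.

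**Working it through.** The Table 8 p-values and Table 10 coefficients need patient-level data and cannot be reproduced. The checks below use the reported quartiles. I read Table 10 as correlating the squat delta with the balance delta, as its title indicates.

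**1. How many finished at the limit.** If 45 is the maximum and n = 20, a lower quartile of 45 (mean of the 5th and 6th ordered values) needs the 5th value to be 45. So at most 4 are below and at least 16 of 20 (80%) are at the limit. For any n from 14 to 20 the minimum share is 76.5% or more (13 of 17 is the lowest). Since scores are averages, these patients would have reached the limit on every attempt averaged.

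**2. Reported delta against 45 minus baseline.** If every final value were 45, the delta quartiles would be 45 minus the baseline quartiles in reverse order. Example, A right, baseline 30.0 (18.25-45.0): 45 - 30.0 = 15.0; 45 - 45.0 = 0; 45 - 18.25 = 26.75.

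| Cell | Baseline | 45 minus baseline | Reported delta |
|---|---|---|---|
| A right | 30.0 (18.25-45.0) | 15.0 (0-26.75) | 11.5 (0-25.5) |
| B right | 40.0 (18.25-45.0) | 5.0 (0-26.75) | 7.5 (0-30.0) |
| A left | 29.5 (15.75-44.0) | 15.5 (1-29.25) | 9.5 (0-21.5) |
| B left | 25.75 (14.5-45.0) | 19.25 (0-30.5) | 20.0 (0-30.0) |

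The match is close for B left and fair for A right. A left falls short by 6.0 s (median) and 7.75 s (upper quartile).

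With a true limit and the same 20 patients at both visits, no delta can exceed 45 minus baseline, so no delta quartile can exceed the third column. Three values do: B right median 7.5 v 5.0, B right upper quartile 30.0 v 26.75, and B left median 20.0 v 19.25. Either the final set is not the same 20 patients or some final times exceeded 45.

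**3. What the delta then measures.** Simulation with assumed inputs: n = 20, baseline interpolated through the reported quartiles with a minimum of 3 s, and 0, 10 or 20% of finals placed at random between baseline and 45. The median Spearman correlation of delta with baseline is -1.00 with none below 45, about -0.98 to -0.99 with 10% below, and about -0.95 to -0.98 with 20% below.

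The Mann-Whitney rejection rate at 0.05 is 4 to 5% when the arms are alike. It is about 6% when A has none and B has 20% below 45, the widest gap that step 1 allows at n = 20.

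**4. Table 10.** The 95% CI is tanh(atanh(r) ± 1.96/√(n - 3)). The arm difference is z = [atanh(rA) - atanh(rB)] / √(2/(n - 3)), which has denominator √(2/17) = 0.343 at n = 20. Open eyes, right: (0.630 - 0.122)/0.343 = 1.48, p = 0.14. Fisher z is an approximation for Spearman coefficients, more so with many ties.

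| Balance | A (95% CI, n = 20) | B (95% CI, n = 20) | p for difference, n = 20 | n = 17 | n = 15 |
|---|---|---|---|---|---|
| Open, right | 0.558 (0.153 to 0.802) | 0.121 (-0.340 to 0.535) | 0.138 | 0.179 | 0.213 |
| Open, left | 0.554 (0.148 to 0.800) | 0.110 (-0.350 to 0.527) | 0.134 | 0.174 | 0.208 |
| Closed, right | 0.390 (-0.063 to 0.710) | 0.009 (-0.435 to 0.450) | 0.240 | 0.287 | 0.324 |
| Closed, left | 0.008 (-0.436 to 0.449) | -0.244 (-0.620 to 0.223) | 0.454 | 0.496 | 0.529 |

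Closed-eyes balance, with final medians of 23.5 to 30.0 s, is not at a ceiling. In A its coefficients have p = 0.09 and 0.97 at n = 20.

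**The case against.** The limit is inferred, and the test description is not in the available text. The table also does not fit a simple model of a 45 s limit with 20 patients throughout, because three B values exceed what that model allows. The final n may be below 20: baseline Kujala and squat quartiles often end in .5, while every final and delta value for them is whole. All of this stands. It is why the p-values above are conditional and why the limit and the final n must be stated. A smaller final set would leave the ceiling in place and make the p-values larger.

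A reader might go further and infer three things that the documents do not support.

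- *That the open-eyes delta measures nothing but baseline.* Up to 4 of 20 per cell may be below 45, and A left departs from 45 minus baseline by 6 to 8 s. A patient who goes from 18 s to 45 s has also improved; the delta is then a lower bound on the gain.
- *That the between-arm test is invalid or has misled the conclusions.* A shared ceiling costs power and leaves the size of the test intact. The SAP draws no arm difference in balance from these p-values.
- *That the strength-balance statement has no support at all.* The SAP puts the weight on open eyes but does not rely on it alone, and A exceeds B in all four rows of Table 10. That support is weak and untested, but it exists. Nor does a ceiling common to both arms by itself explain 0.558 in A against 0.121 in B.

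The missing test of the arm difference is a separate fault and would remain without any ceiling. The trial's closing conclusion concerns pain and quality of life, so the consequence is confined to a secondary claim.

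**Conclusion.** The point holds in limited form. A ceiling at 45 s is the evident reading of Table 8. On that reading at least three quarters of each cell finished at the limit, and the open-eyes delta is mostly baseline deficit in another form. Two consequences follow.

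- The values 0.916 and 0.282 carry little information on a treatment effect and must not be read as equal balance.
- The inference that strength gain improves balance, and more so with core exercise, should not lean on 0.558 and 0.554. The measure that is free of the ceiling gives weaker coefficients, and no row shows a clear difference between arms (p = 0.13 to 0.45 at 20 per arm, larger at smaller n).

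This rests on a limit of 45 s and, for the p-values, on 20 patients per arm at the end. Neither is stated. Without patient-level data it remains likely, not shown, that baseline deficit drives the open-eyes coefficients. The pain and Kujala results are unaffected.

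**What to change.** 1. State the maximum test time and the number analysed at the end in each arm. Explain why the B delta quartiles exceed 45 minus baseline (right median and upper quartile, left median).
2. Report the number at the limit by arm, leg and visit. Analyse open eyes as reached/not reached or as right-censored time, adjusted for baseline.
3. Give Table 10 with confidence intervals and a test of the difference between arms. Label the coefficients on one scale: 0.558 is called strong, while -0.545 in the Q-angle section is called moderate.
4. Rest any strength-balance statement mainly on closed eyes, and withdraw the conclusion that the correlation is stronger when core exercises are included.

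The cost is a small re-analysis of existing data and the loss of one secondary claim.
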